In patients with refractory anaplastic astrocytoma, the most frequently occurring adverse reactions were nausea, vomiting, headache, and fatigue. The adverse reactions were usually NCI Common Toxicity Criteria (CTC) Grade 1 or 2 (mild to moderate in severity) and were self-limiting, with nausea and vomiting readily controlled with antiemetics. The incidence of severe nausea and vomiting (CTC Grade 3 or 4) was 10% and 6%, respectively. Myelosuppression (thrombocytopenia and neutropenia) was the dose limiting adverse reaction. It usually occurred within the first few cycles of therapy and was not cumulative. Myelosuppression occurred late in the treatment cycle and returned to normal, on average, within 14 days of nadir counts. The median nadirs occurred at 26 days for platelets (range: 21-40 days) and 28 days for neutrophils (range: 1-44 days). Only 14% (22/158) of patients had a neutrophil nadir and 20% (32/158) of patients had a platelet nadir, which may have delayed the start of the next cycle. Less than 10%

of patients required hospitalization, blood transfusion, or discontinuation of therapy due to myelosuppression.

In clinical trial experience with 110 to 111 women and 169 to 174 men (depending on measurements), there were higher rates of Grade 4 neutropenia (ANC <500 cells/ μ L) and thrombocytopenia (<20,000 cells/ μ L) in women than men in the first cycle of therapy (12% vs. 5% and 9% vs. 3%, respectively).

In the entire safety database for which hematologic data exist (N=932), 7% (4/61) and 9.5% (6/63) of patients over age 70 experienced Grade 4 neutropenia or thrombocytopenia in the first cycle, respectively. For patients less than or equal to age 70, 7% (62/871) and 5.5% (48/879) experienced Grade 4 neutropenia or thrombocytopenia in the first cycle, respectively. Pancytopenia, leukopenia, and anemia have also been reported.

Contraindication:

Temozolomide is contraindicated in patients who have a history of hypersensitivity reaction (such as urticaria, allergic reaction including anaphylaxis, toxic epidermal necrolysis, and Stevens-Johnson syndrome) to any of its components. TEMODAR is also contraindicated in patients who have a history of hypersensitivity to DTIC, since both drugs are metabolized to 5-(3-methyltriazen-1-yl)-imidazole-4-carboxamide (MTIC).

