For grade 2 events of increased bilirubin, AST, ALT, dyspnea, or DIC, the dose of SGT-53 and Temozolomide can be held for up to two weeks. If the grade 2 event reduces at least to grade 1 within two weeks, then infusion of SGT-53 and Temozolomide can resume at the same dose per calendar at incident week + 1-2 weeks (i.e., treatment would be made up and moved 1-2 weeks later).

For non-hematological events other than increased bilirubin, AST, ALT, dyspnea, or DIC, participants who develop a > or = grade 2 toxicity (except for alopecia, fever, chills or hypotension that respond to treatment) or grade 3 fatigue will discontinue twice-weekly infusions until the toxicity level reduces to at least grade 1. Infusions will be held for one week intervals, and infusions that are withheld will be made-up (i.e. moved 1-2 weeks later). If the toxicity does not resolve within two weeks, study drug will be discontinued.

A minimum of 2-week rest period will be required if there is grade III or greater non-hematologic toxicity related to SGT-53/Temozolomide that cannot be controlled with supportive medications/measures. After the minimum 2-week rest period and the toxicity has resolved to a grade II or better, the patient will resume taking the drug at a reduced dose level as shown in Table 9.7.2b below.

Subjects who receive less than four of twelve of the intended drug infusions, due to experiencing these grade 2 events that have not resolved as described above, and that are determined by the PI to be at least probably related to SGT-53, will be considered to have experienced a DLT.

Patients forced to discontinue temozolomide due to a temozolomide-related toxicity (e.g., grade 3, 4 hypersensitivity) will be removed from the study.

^{**}Note that infusion reactions are discussed in detail in Section 9.3.2.

9.7.2. Temozolomide

Table 9.7.2a. reviews management of hematologic toxicities associated with Temozolomide treatment. Note that there are no dose adjustments for anemia.

	Grade 1	Grade 2	Grade 3 or Grade 4
Neutropenia	< LLN to	<1500 to	Grade 3: <1000 to 500/mm ³
	$1500/\text{mm}^3$	$1000/\text{mm}^3$	Grade 4: <500/mm ³
			If resolves to grade ≤ 2 within 14
	Proceed at	Proceed at	days, rechallenge at same dose of
	current dose	current dose	SGT-53, and reduce dose of TMZ
			in increments after each event
			according to Table 9.7.2b below,
			i.e. in Cycle 1reduce to 100
			mg/m ² after the first event, in
			Cycle 2 reduce to 150 mg/m2

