			after the first event, if recurs
			reduce to 100 mg/m ² etc
			If recurs at lowest dose of TMZ
			(100 mg/m ² or less), withdraw
			from study. If at any time it does
			not resolve within 14 days,
Tr1 1	ZUNA	<75 000 to	withdraw from study.
Thrombo-	<lln td="" to<=""><75,000 to	Grade 3: <50,000 to 25,000/mm³	</lln>	<75,000 to	Grade 3: <50,000 to 25,000/mm ³
cytopenia	$75,000/\text{mm}^3$	50,000/mm ³	Grade 4: <25,000/mm ³
	Proceed at	Proceed at	If resolves to grade ≤ 2 within 14 days, rechallenge at same dose of
	current dose	current dose	SGT-53, and reduce dose of TMZ
	current dosc	current dosc	in increments after each event
			according to Table 9.7.2b below,
			i.e.in Cycle 1 reduce to 100
			mg/m^2 after the first event, in
			Cycle 2 reduce to 150 mg/m ² after
			the first event, if recurs reduce to
			100 mg/m ² etc
			If recurs at lowest dose of TMZ
			(100 mg/m ² or less), withdraw
			` '
			not resolve within 14 days,
			withdraw from study.
			(100 mg/m ² or less), withdraw from study. If at any time it does not resolve within 14 days,

Table 9.7.2.b Dose de-escalation for TMZ:

Treatment Cycle	Agent	Schedule	Level	Level	Level
			0 (Target Dose)	-1	-2
Cycle 1	TMZ	Days 9-13	150 mg/m^2	100mg/m^2	
Cycle 2 onwards		Days 9-13	200 mg/m ²	150 mg/m ²	100 mg/m^2

In the event of grade III or higher toxicity associated with TMZ after cycle 1, treatment will be interrupted and patient monitored for resolution of toxicity, with subsequent reinitiation of treatment. TMZ dosing will resume after complete resolution of toxicities to Grade II or less.

The dose of Temozolomide will only be escalated to 200 mg/m2 if the patient meets the following criteria: If the CTC nonhematologic toxicity for Cycle 1 is \leq Grade 2 (except for alopecia, nausea, and vomiting, diarrhea, or fever, chills or hypotension which respond promptly to treatment and lasts less than 24 hours), absolute neutrophil count (ANC) is \geq 1,500/mm³, and the platelet count is \geq 100,000/mm³. The dose remains at 200 mg/m2 per day for the first 5 days of each subsequent cycle except if toxicity occurs. If the dose was not escalated at Cycle 2, escalation should not be done in subsequent cycles.

If more than a 2 week delay is required to meet hematologic parameters for treatment, the patient must be removed from study and replaced.

9.7.3. Dose de-escalation for SGT-53:

Permitted dose modifications for SGT-53

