10.2. Evaluation During Study

The starting dose of SGT-53 will be 3.6 mg of DNA. If necessary, dose de-escalation for SGT-53 will proceed according to the dose de-escalation scheme in Table 9.7.3 above. Assessment of DLTs will be made based on the first cycle (4 weeks of treatment). At the end of the first cycle, if no DLT are observed, additional patients may be enrolled and treated simultaneously. If the first patient experiences a DLT in the first cycle (4 weeks), then only one additional patient will be enrolled and evaluated for DLT. If the second patient does not experience DLT in the first cycle (4 weeks), then additional patients may be enrolled simultaneously.

10.2.1. Patients with Optional Surgical Resection for Tumor Analysis:

Beginning 5 days prior to scheduled surgical resection of their recurrent glioblastoma, patients will initiate 3.6mg DNA dosing/infusion with SGT. Dosing will continue through the day before surgery.

• One portion of the surgical section will be saline rinsed and flash frozen for measurement of exogenous wt p53 in tumor tissue, one portion will be immediately formalin-fixed for evaluation of PD biomarkers of activity of SGT-53 including but not limited to Annexin V and TUNEL staining. In addition, one portion of fresh tissue will be used for flow cytometry and/or immunohistochemistry analysis to determine the level of apoptosis in Cancer Stem Cells (CSC) and bulk tumor cells. Any remaining tumor tissue from an earlier procedure will be collected and stored in a research tissue bank at Georgetown University or the clinical site.

Following surgery, an MRI scan should be done no later than 72 hours from the time of surgery.

Following recovery from surgical resection (POD ~14-21), patients will restart SGT-53 and TMZ on the morning of Cycle 1 Day 1 (C1D1). Each cycle will consist of 28 days. Patients will return to the clinic for twice weekly (every 3rd or 4th day) infusions of SGT-53 for three weeks (see treatment schedule diagram in section 9.1.1). Temozolomide will be taken daily by mouth daily on days 9-13 of each cycle. During week 4 of each cycle the patient will not receive any treatments. Patients will return to the clinic on Day 29 (C2D1) and Day 57 (C3D1) for evaluation. If the drug has been well tolerated, continued dosing will be permitted even if they appear to be progressing.

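### The first-patient safety gate is read on temozolomide day 20, before both quoted median nadirs, and the one sentence that says who has a DLT has no blood-count criterion

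*Combined protocol and SAP*

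**What the plan says.** Section 10.2 (Evaluation During Study) sets the gate: "Assessment of DLTs will be made based on the first cycle (4 weeks of treatment", and then "At the end of the first cycle, if no DLT are observed, additional patients may be enrolled and treated simultaneously". If the first patient has a DLT, one more patient is enrolled and judged over the same four weeks. Nothing is said about a DLT in that second patient.

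The pointers to the DLT definition differ. Sections 8.1 and 10.5 name Section 9.7. Section 11.7 names Section 9.4, which covers discontinuation and withdrawal and defines no DLT. The only sentence that says who has had a DLT is in Section 9.7.1: "Subjects who receive less than four of twelve of the intended drug infusions, due to experiencing these grade 2 events", where the events are unresolved and judged at least probably related to SGT-53. The paragraphs before it show which events are meant: bilirubin, AST, ALT, dyspnea, DIC and other non-hematologic toxicity.

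Blood counts are handled elsewhere in Section 9.7. In Table 9.7.2a, grade 3 or 4 counts (for platelets, "Grade 3: <50,000 to 25,000/mm"³ and below) lead to a temozolomide reduction or to withdrawal. In Table 9.7.3 they lead to holding or reducing SGT-53. For long delays Section 9.7.2 says: "If more than a 2 week delay is required to meet hematologic parameters for treatment, the patient must be removed from study and replaced". None of these is called a DLT.

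On timing, Section 7.1 reports for anaplastic astrocytoma: "The median nadirs occurred at 26 days for platelets (range: 21-40 days) and 28 days for neutrophils (range: 1-44 days".

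**The concern.** Section 7.1 describes myelosuppression as a known dose-limiting toxicity of temozolomide that comes late in the cycle. The protocol describes SGT-53 in patients as a single agent and with docetaxel, but not with temozolomide. The purpose of the gate is to see how the first patient tolerates the combination before others are treated in parallel.

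If the gate is read before the counts are expected to reach their lowest point, and its criterion names no count, it can be passed with little evidence on the most expected toxicity. Taken literally, the Section 9.7.1 sentence would let enrolment open even after a grade 4 platelet count in the first patient.

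**Working it through.** **Inputs.** Four-week first cycle and gate at its end (10.2). Temozolomide on cycle days 9-13 (5 and 10.2). Cycle 1 blood counts on days 1, 8, 15 and 22, and the same days in cycle 2 (18.1.1). Nadirs from 7.1. Assumption: nadir days run from the first temozolomide dose, counted as day 1, because the protocol gives no origin.

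**1. The plan's own calendar.** 4 × 7 = 28, so cycle 2 day 1 is day 29 and cycle 3 day 1 is day 57. Both agree with 10.2.

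**2. Where the gate falls.** Temozolomide day = study day − 8.
- Gate: 28 − 8 = day 20 (day 21 if read at the day 29 visit).
- Last scheduled count inside it: 22 − 8 = day 14.

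**3. Where the nadirs fall.** Study day = 8 + temozolomide day.

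| | Median | Range | Median after gate | Median after last count |
|---|---|---|---|---|
| Platelets | 8 + 26 = 34 | 29 to 48 | 34 − 28 = 6 days | 34 − 22 = 12 days |
| Neutrophils | 8 + 28 = 36 | 9 to 52 | 36 − 28 = 8 days | 36 − 22 = 14 days |

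The whole quoted platelet range lies after day 28. The neutrophil range does not, so some neutrophil nadirs can fall inside the window.

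**4. Other time origins.** With the first dose as day 0, the medians are study days 35 and 37. Counted from the last dose (day 13), they are 39 and 41. The gate comes first in every case.

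**5. Other readings of DLT.** If all of 9.7 is the definition, the count tables apply, but the dates in step 3 do not change. If 9.4 is meant, a grade 4 event unresolved for 14 days must begin by 28 − 14 = study day 14 (temozolomide day 6) to be recognised by day 28.

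**6. Exposure of the next patient.** A patient who starts on the first patient's day 29 takes a first temozolomide dose on that patient's day 29 + 8 = 37. The first patient's counts on days 29 and 36 are due before then.

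**7. What one clean patient shows.** With 0 events in 1 patient, the one-sided 95% upper limit solves 1 − p = 0.05, so p = 95%.

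**8. How often temozolomide alone could meet a count criterion.** For patients up to age 70, 7.1 reports: "7% (62/871) and 5.5% (48/879) experienced Grade 4 neutropenia or thrombocytopenia in the first cycle, respectively". Adding the patients over 70:
- neutropenia (4 + 62)/(61 + 871) = 66/932 = 7.1%;
- thrombocytopenia (6 + 48)/(63 + 879) = 54/942 = 5.7%.

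From full to no overlap, either event occurs in 7.1% to 12.8%. By sex, grade 4 neutropenia and thrombocytopenia were higher "in women than men in the first cycle of therapy (12% vs. 5% and 9% vs. 3%, respectively". That gives 12% to 21% in women and 5% to 8% in men. Grade 3 events come on top, and the documents give no first-cycle rate for them.

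**The case against.** The strongest reply is that Section 9.7.1 should not be read alone. Section 4.6.4 keeps patients evaluable when a first-cycle interruption or reduction is due to a DLT, which presumes DLTs that lead to dose reduction. Table 9.7.2a prescribes just such a reduction in cycle 1 for grade 3-4 counts. Two of the three pointers name all of Section 9.7, and the sentence in 10.2 just before the DLT rule refers to Table 9.7.3, a count table. The 9.7.1 sentence also counts twelve infusions where one cycle has six, so it fits the gate poorly. This stands as a reason for caution. A reader might infer that the protocol deliberately excludes low counts from the DLT definition, and the documents do not support that. They leave it unclear, and the broader reading does not change the dates.

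A second reply is that little harm follows. Step 6 shows that two more counts are due before anyone admitted through the gate takes temozolomide. Entrants must have tolerated earlier temozolomide. In Phase Ia, neutropenia was grade 1-2 and thrombocytopenia grade 1. Eight Phase Ib patients received SGT-53 with docetaxel, described as relatively well tolerated. Weekly counts, the dose rules, SAE reporting of grade 4 events and the DSMB's power to halt accrual all remain. This largely stands. But the accrual powers are discretionary, grade 3 is not automatically an SAE, and no text ties them to the gate.

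A third reply is that nadir is not onset: a count can cross grade 3 before its lowest point. That stands. A reader might infer that the gate would miss the first patient's myelosuppression. The documents give only medians and ranges, so no detection rate can be computed and that inference is not available.

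**Conclusion.** The point holds as a minor one. The gate is read 6 days before the quoted platelet median, 8 days before the neutrophil median and before the whole quoted platelet range, and its one explicit DLT sentence has no count criterion. The timing part survives every reading of the definition and every time origin tried. The criterion part is an ambiguity that the text does not resolve.

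It would be tempting to conclude that later patients are put at serious risk. The documents do not support that, given the temozolomide lag and the remaining safeguards. One patient would exclude little even with a better gate.

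The result assumes an undelayed schedule and nadir data from anaplastic astrocytoma applied to recurrent glioblastoma. The documents do not say whether the gate had already been used by Amendment 6. If it had, the change matters only where the gate is still to be applied.

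**What to change.** In Section 10.2, replace all four time phrases (the two that open the DLT rule, and those for the first and second patient) with one window, for example:

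> The gate window runs from cycle 1 day 1 through the first scheduled CBC on or after temozolomide day 28 (first dose = day 1) and before the second temozolomide course. Without delays this is cycle 2 day 8, study day 36. If the first temozolomide dose is delayed, the window moves with it. For this gate, grade 3-4 neutropenia (ANC <1000/mm³) or thrombocytopenia (platelets <50,000/mm³), as in Table 9.7.2a, on any count in the window is a DLT, regardless of attribution. If there is no DLT once that CBC is reviewed, simultaneous enrolment may open. After a DLT, one further patient is assessed over the same window. A patient who leaves before the window ends without a DLT does not clear the gate, and the next patient takes that place. If the second patient also has a DLT, the DSMB advises before enrolment continues.

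Tying the window to temozolomide matters. If cycle 1 slips so that the first dose is on day 16, the medians move to days 15 + 26 = 41 and 15 + 28 = 43, and a fixed day 36 would be only temozolomide day 21. On schedule, day 36 precedes the second course (days 37-41). Section 9.6 keeps assessments going while dosing is held. Later parts of both ranges (to days 48 and 52) stay uncovered. With the first dose as day 0, day 36 is one day short of the neutrophil median.

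**Cost.** A few sentences, with no new test or visit. Opening moves by 36 − 28 = 8 days, or by 72 − 56 = 16 days if a second patient is needed under either rule. If only the new criterion is met, at the day 36 count, opening moves from day 28 to about day 72, which is 44 days plus the time to find the second patient. Temozolomide alone can cause this, and the documents give no firm upper bound on how often. The mismatch between twelve infusions and a six-infusion cycle is a separate repair.

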Surgical resection of recurrent or progressive tumor for tumor analysis is an optional procedure. In these individuals SGT-53, at a dose of 3.6 mg DNA per infusion, will be administered twice (on days -1 and -3) in the week prior to surgery. Surgical resection is Day 0. 14-21 days post operatively and having recovered from the effects of surgery, the patients will then start cyclical TMZ with

Study Subject Population

The study population is subjects with confirmed glioblastoma or gliosarcoma who have proven tumor recurrence or progression. Study participants must have measurable disease on imaging studies and Eastern Oncology Cooperative Group (ECOG) performance status 0-2 (Karnofsky performance status [KPS] > 60). Tumors amenable to surgical resection is not a requirement.

Study Procedures

After screening, SGT-53 study drug will be administered by iv infusion twice weekly, beginning on Day 1 of a 28 day cycle as described above with Temozolomide administered orally daily on days 9-13 of each cycle at 150mg/m2 (cycle 1), and 200mg/m2 as tolerated from cycle 2 onwards provided the patient meets the criteria for non-hematological toxicity, ANC and platelet counts. . In those patients who have undergone the optional surgical resection, the 1st cycle of SGT-53 and TMZ will commence 14-21 days post operatively and after having recovered from the effects of surgery. Following first infusion of study agent on Day1, participants will be evaluated weekly for a total of at least 12 weeks. At these weekly study visits, participants will have a physical examination, routine chemistry, and complete blood count.

- After screening, SGT-53 will be administered by iv infusion twice during the week prior to surgical resection of the tumor. 14-21 days post operatively and having recovered from the effects of surgery, SGT-53 study drug will be administered by iv infusion twice weekly beginning on Day 1 of a 28 day cycle as described above.
- A sample of the tumor obtained at resection will be employed to assess levels of exogenous wild type (wt) p53 cDNA to validate targeting.

Primary Study Outcome Measures

• To evaluate the 6 month PFS in patients treated with SGT-53 in combination with Temozolomide.

Secondary Study Outcomes

- To assess safety of the combination of SGT-53 and Temozolomide by analysis of adverse experiences, clinical laboratory tests and physical examinations.

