If optional surgical resection will be performed, SGT-53 will be administered on day -3 and day -1 prior to surgery. Surgical resection of recurrent or progressive tumor is Day 0. 14-21 days post operatively and having recovered from the effects of surgery the patients will then start cyclical TMZ with SGT as described above. A maximum of 6 patients will be have this optional testing. Once the presence of exogenous wtp53 from SGT-53 is demonstrated in the resected tumor of 3 patients, the option for surgical resection for tumor analysis will no longer be offered.

4.6.1. Dose Selection:

In the Phase 1a study of SGT-53 as a single agent the nanocomplex was administered twice weekly for five consecutive weeks. No patient received more than 10 infusions in a single cycle. Two cycles of 10 infusions were administered to one patient.

In various clinical trials Temozolomide has been administered daily for 5 days in one 28 day period. To optimize effectiveness of the potential chemosensitization of SGT53, SGT53

treatment will be given three times prior to the start of temozolomide treatment. Pre-clinical studies have shown that the wtp53 tumor suppressor gene delivered by the SGT-53 nanoparticle functions to sensitize tumors to the chemotherapeutic agent, making them more responsive to the drug. Thus, it is critical that p53 be expressed when temozolomide is administered in order to have the benefit of the SGT-53. Using the proposed schedules, SGT-53 is being expressed at the start of temozolomide treatment. For patients who undergo optional surgical resection for tumor analysis, two doses of SGT-53 will be administered in the week prior to surgical resection of the tumor to demonstrate the presence of exogenous wtp53 in the tumor to validate SGT-53 crossing the BBB and targeting the tumor.

4.6.2. Treatment Duration:

Patients will receive a total of 3 cycles of TMZ in combination with SGT. Patients who are responding to treatment (at least stable disease by RANO) may receive three additional cycles of SGT-53/Temozolomide therapy at investigator's discretion. Alternatively, they may continue on Temozolomide alone at investigator's discretion.

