Reverse transcription PCR to determine transgene expression is not applicable for these studies because it would not be able to unequivocally establish that the p53 protein detected was from the exogenous transgene. In contrast, since we have designed primers that included part of the plasmid vector backbone, only the exogenous DNA is amplified. This DNA PCR approach was used to detect the presence of the transgene in the tumors in the Phase I trial (See Figures 16 and 17 in Section 4.4.1.1) and will be used for these studies. The presence of at least 30 copies of exogenous p53 in the tumors sample will be considered positive evidence of drug penetration.

All of the patients in the trial will receive the same dosing of the combination of SGT-53 and TMZ (6 doses of SGT-53 and 5 doses of TMZ every 4 weeks for three 4 week cycles) and thus patients with or without surgical resection for tumor analysis will be used for the Simon two stage calculation. Even for the patients who undergo the optional surgical resection for tumor analysis PFS6 is the primary endpoint. No TMZ will be administered during the time these patients receive the two doses of SGT-53 prior to the resection. Exogenous p53 expression is transient. The patients who receive surgery will not begin treatment for 2-3 weeks post-surgery. Previous studies have demonstrated that there is no indication of the exogenous wtp53, even by DNA PCR, after this length of time. Thus, there will be no additional residual DNA present from the two pre-surgery doses of SGT-53 by the time the combination therapy being evaluated is initiated.

According to the Simon Minimax design, our study, with its sample size of n = 26, has a 10% probability of rejecting (a) the hypothesis of a PFS6 15% (P0) (the historical PFS6 rate) and a 70% probability of accepting (1-b) the hypothesis of a PFS-6 of 30% (P1). If two, or fewer of the first 18 patients were progression free at 6 months, PFS-6 would be considered <15% and the study terminated. Otherwise, the study would be completed, the accrual target being 26 patients. If six or fewer of the 26 patients were progression-free at 6 months, then no further investigation of the treatment regimen would be considered warranted. PFS6 and secondary endpoints progression free survival and overall survival will be evaluated using the Kaplan-Meier product-limit survival curve methodology.

4.6.5. Study Objectives:

Primary:

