• To evaluate the 6 month PFS in patients treated with SGT-53 in combination with Temozolomide.

Secondary:

- To assess safety of the combination of SGT-53 and Temozolomide.
- To evaluate progression free survival (PFS) and OS in patients in patients with recurrent or progressive glioblastoma or gliosarcoma treated with SGT-53 in combination with Temozolomide.
- To determine the anti-tumor activity of the combination of SGT-53 and Temozolomide based upon the RANO criteria in patients with recurrent or progressive GBM tumors.
- To assess nanoparticle delivery to tumor site by analysis of the presence of exogenous wt p53 in the tumor (optional procedure).
- To assess induction of apoptosis by SGT-53 in the tumor by flow cytometry or histology (optional procedure).

5. INVESTIGATIONAL PLAN

This is a prospective open label single arm Phase II study to assess the efficacy of nanoparticle delivery to tumor site of exogenous wt p53. This trial will also evaluate the safety, tolerability,

toxicity and efficacy of SGT-53 (given in combination with temozolomide) on PFS and OS in adult patients with recurrent Glioblastoma or gliosarcoma.

The study population (26 patients) will be registered through and treated at: MD Anderson Cancer Center, Texas, USA and China Medical University Hospital, Taichung, Taiwan, based on Inclusion/Exclusion Criteria (see Sections 6.1. and 6.2.)

Although an MTD for SGT-53 was not reached in the previous Phase Ia trial, the highest dose tested was 3.6mg of DNA. This is the dose of SGT-53 that will be employed in this trial. Below is the schedule of treatment:

Cycles 1-3 (1 Cycle is 28 days)

- Day 1: SGT infusion
- Day 4: SGT infusion
- Day 8: SGT infusion
- Days 9-13-: TMZ (150mg/m2 (cycle 1) increasing to 200mg/m2 (from cycle 2 onwards) as tolerated, provided the patient meets the criteria for non-hematological toxicity, ANC and platelet counts (see 9.7.2)
- Day 11: SGT infusion
- Day 15: SGT infusion
- Day 18: SGT infusion
- Days 19-28: No treatment

Cycles 4-6: Patients who are responding to treatment (at least stable disease by RANO) may receive three additional cycles of SGT-53/Temozolomide therapy at investigator's discretion. Alternatively, they may continue on Temozolomide alone at investigator's discretion.

When the Patient has Undergone Optional Surgical Resection For Tumor Analysis (4-6 patients only):

- SGT infusion on days -3 and -1
- Surgery on Day 0

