Patients will be monitored for response and disease progression with MRI brain scans every 2 cycles (8 weeks) and/or at the end of cycle 3, or earlier if progressive disease is suspected.

All patients who participate in this study will continue treatment with SGT-53 and TMZ after surgery. The following conditions should be satisfied before initiation of treatment with SGT:

- 1) They have recovered from the effects of surgery including adequate wound healing.
- 2) A brain MRI should be done no later than 72 hours in the immediate post-operative period to best assess the extent of residual measurable disease post-operatively.
- 3) The patient has followed the study requirements for birth control and pregnancy testing since the initial pre-operative doses of SGT and TMZ.
- 4) Post-operatively, patients must have adequate bone marrow function (absolute neutrophil count > 1,500/ μ L and platelet count of >100,000/ μ L), normal coagulation profile (PT/PTT), adequate liver function (SGPT, SGOT, and alkaline phosphatase <2.5 times upper limit of normal and bilirubin < 1.5 X upper limit of normal), adequate renal function (BUN or creatinine <1.5 times upper limit of institutional normal within 7 days prior to starting therapy.
- 5) The patient continues to meet all the eligibility criteria of the study outlined above.

10.2.2. Patients Not undergoing Surgical Resection:

Patients who have had surgery for recurrent glioblastoma will follow the guidelines listed above for patients with optional surgical resection for tumor analysis.

If no surgery has been performed, patients will start SGT-53 and TMZ on the morning of Cycle 1 Day 1 (C1D1). Each cycle will consist of 28 days. Patients will return to the clinic for twice weekly (every 3rd or 4th day) infusions of SGT-53 for three weeks (see treatment schedule diagram in section 9.1.1). Temozolomide will be taken daily by mouth daily on days 9-13 of each cycle. During week 4 of each cycle the patient will not

receive any treatments. Patients will return to the clinic on Day 29 (C2D1) and Day 57 (C3D1) for evaluation. If the drug has been well tolerated continued dosing will be permitted even if they appear to be progressing.

Patients will be monitored for response and disease progression with MRI brain scans every 2 cycles (8 weeks) and/or at the end of cycle 3 or earlier if progressive disease is suspected.

10.2.3. All Patients:

Evaluations done at each clinic visit are detailed in Section 18.1.

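### Section 10.2.1 starts pre-operative SGT-53 five days before resection with no infusion count; the rest of the protocol gives two infusions on days -3 and -1

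*Combined protocol and SAP*

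**What the plan says.** Section 10.2.1, which covers patients having the optional resection, opens with: "Beginning 5 days prior to scheduled surgical resection of their recurrent glioblastoma, patients will initiate 3.6mg DNA dosing/infusion with SGT". It adds: "Dosing will continue through the day before surgery". It gives no number of infusions and no interval between them.

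Elsewhere the days are explicit:

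- Synopsis: SGT-53 "will be administered twice (on days -1 and -3) in the week prior to surgery".
- Section 4.6: "SGT-53 will be administered on day -3 and day -1 prior to surgery". The same section fixes the numbering: "Surgical resection of recurrent or progressive tumor is Day 0".
- Section 5, and again the Section 9 treatment plan: "SGT infusion on days -3 and -1".
- Calendar 18.1.2: SGT-53 is marked before surgery at D-3 and D-1 only, and the pre-surgery block has columns D-3, D-2 and D-1 and no others.

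On temozolomide, Section 4.6.4 states: "No TMZ will be administered during the time these patients receive the two doses of SGT-53 prior to the resection". The calendar marks none before Day 9 of Cycle 1. Yet condition 3 of Section 10.2.1, which concerns birth control and pregnancy testing, covers the period "since the initial pre-operative doses of SGT and TMZ". The same section also speaks of patients restarting both agents on Cycle 1 Day 1.

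**The concern.** A site reading Section 10.2.1 and a site reading Section 9 would give the first SGT-53 infusion on different days before neurosurgery, and possibly a different number of infusions.

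The first infusion carries its own monitoring: the 23-hour observation in Section 9.3.3, ECGs at 2 hours and about a day later, and coagulation tests at about 20 hours (Section 10.2.3). The surgical calendar places the ECGs on D-3 and D-2 and the coagulation tests on D-2. A first infusion on day -5 would fall on a day the calendar does not contain. Each infusion also brings the premedication in Section 9.2, so the number of infusions sets that pre-operative exposure too.

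The tumor result is at stake as well. Section 8.2 calls delivery positive if at least 3 patients' tumors contain the exogenous gene, with at most 6 patients tested. Section 4.6.4 sets the threshold at 30 copies. With so few tumors, the result is interpretable only if every specimen comes from one defined exposure.

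The temozolomide phrase raises a narrower question. A secondary objective is apoptosis induced by SGT-53. If any temozolomide were given before resection, apoptosis in the specimen could not be attributed to SGT-53.

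**Working it through.** No sample-size, power or error-rate figure is involved, so there is no plan figure to reproduce. The check is a comparison of text plus day arithmetic with surgery as Day 0.

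**Step 1. SGT-53 before surgery**

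| Place | First dose | Last dose | Number of infusions |
|---|---|---|---|
| Section 10.2.1 | day -5 | day -1 | not stated |
| Synopsis | day -3 | day -1 | 2 |
| Section 4.6 | day -3 | day -1 | 2 |
| Section 5 | day -3 | day -1 | 2 |
| Section 9 | day -3 | day -1 | 2 |
| Calendar 18.1.2 | D-3 | D-1 | 2 |

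Difference in first dose: (-3) - (-5) = 2 days. Difference in last dose: 0 days. Descriptions that speak only of the week before surgery, such as those in Sections 4.5.1 and 4.6.1, fit either start day and do not settle the matter.

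**Step 2. Number of infusions under 10.2.1**

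The documents do not give it. The following spacings are assumptions, shown only for the range:

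- Day -5 and day -1 (a 4-day gap, as allowed within treatment cycles): 2 infusions.
- Alternate days (-5, -3, -1): 3 infusions.
- Daily (-5 to -1): 5 infusions.

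The in-cycle spacing of every 3rd or 4th day cannot simply be carried over to fill the gap: days -3 and -1 are 2 days apart, so the other pre-operative schedule does not follow it either.

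**Step 3. Fit with the calendar**

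Monitoring after a first infusion on day -3 falls on D-3 and D-2, where the calendar has it. After a first infusion on day -5 it would fall on D-5 and D-4, for which there are no columns.

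**Step 4. Interval to Cycle 1**

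Cycle 1 starts 14 to 21 days after surgery. From the last pre-operative dose on day -1 this is 14 + 1 = 15 to 21 + 1 = 22 days under both schedules.

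**Step 5. Temozolomide before surgery**

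- Excluded: Section 4.6.4.
- Not listed or not marked: Sections 5 and 9, which list only SGT-53 before surgery, and calendar 18.1.2.
- Referred to as already given: condition 3 of 10.2.1.
- Possibly implied: the restart wording in 10.2.1.
- Ordered, with a dose or day: nowhere.

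**The case against.** The strongest reply is that dosing is set in Section 9, the treatment plan, while Section 10 deals with assessments. Five day-specific statements agree with one another, and one paragraph stands apart. That is fair, and it lowers the chance that a site would follow 10.2.1. It does not remove the conflict: 10.2.1 is the section written for these patients, it also holds the tissue handling and the conditions for starting post-operative treatment, and nothing says which text prevails.

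It can also be said that Section 9.3.3 ties observation to the first infusion and not to a calendar day, so a careful site would move the monitoring. That is true, but the calendar would still not show it.

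Three stronger readings are tempting, and the documents do not support them.

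- A reader might infer that the protocol contains a second regimen with pre-operative temozolomide. It does not: no section orders such a dose. The restart wording is weak evidence, because Section 10.2.2 describes patients without surgery as starting both agents on Cycle 1 Day 1, although temozolomide begins on Day 9 in both groups.
- A reader might infer that pooling the surgical patients in the Simon two-stage analysis is undermined. Section 4.6.4 rests pooling on common dosing from Cycle 1 and on loss of the exogenous DNA over the 2 to 3 weeks after surgery. Step 4 shows that the interval from the last dose is the same either way, so an earlier first SGT-53 dose barely affects the argument.
- A reader might infer that up to five infusions are prescribed. That count comes from an assumed daily spacing.

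Finally, Section 4.6.4 calls the tumor analysis qualitative, in an optional sub-study. That limits the consequence, but a qualitative positive still has to belong to a known exposure.

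**Conclusion.** The point holds as an internal inconsistency in current text. For pre-operative SGT-53, Section 10.2.1 differs from five other places by 2 days in the first dose and leaves the number of infusions unstated; the last dose is the same. It affects at most 6 patients, but it bears on first-infusion monitoring before neurosurgery and on the exposure behind a result that turns on 3 positive tumors.

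The temozolomide reference in condition 3 is a secondary wording conflict with Section 4.6.4. Its consequence for the apoptosis objective arises only if a dose were actually given.

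The 2-day difference depends only on surgery being Day 0, which Section 4.6 states. Any infusion count for 10.2.1 is an assumption. No conclusion is drawn about which schedule is right, and the primary analysis is not called into question.

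**What to change.** Reconcile Section 10.2.1 with the synopsis, Sections 4.6, 4.6.4, 5 and 9, and calendar 18.1.2. Three places in 10.2.1 need attention: the first paragraph, the sentence on restarting both agents after surgery, and condition 3. After the change, one pre-operative SGT-53 schedule with its days and number of infusions, and one statement on whether temozolomide is given before resection, should appear throughout. The calendar columns and first-infusion monitoring marks should match whatever schedule the sponsor confirms.

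The cost is amendment wording; sample size and the analysis do not change. If any patient has already had the resection, the infusion dates and count actually given should be reported next to each tumor result.
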